**Procedures to be conducted as part of the interventions:**

After completing the required testing, participants will be randomly assigned to one of two treatment groups: Healthy Lifestyle and Sleep Education alone (HLSE) or HLSE plus PAP (HLSE-PAP).

- 1. HLSE intervention:** Lifestyle guidelines developed by the American Heart Association and American Diabetes Association for disease prevention and weight loss will be provided to all subjects. Compliance with anti-diabetic medications will be emphasized. In addition, counseling on sleep hygiene using published materials to suggest ways to improve the regularity and duration of sleep, aiming for 7-8 hours of sleep per night. General lifestyle advice relevant for OSA will also be provided, including a recommendation for regular exercise and avoidance of alcohol, particularly near bedtime.
- 2. PAP therapy:** This intervention includes OSA treatment with PAP, titrated using a home-based computerized auto-titration protocol. Participants will have an opportunity to try various PAP mask interfaces in order to optimize fit. Verbal and written directions on the use of these materials will be provided, with instructions reinforced after the initial period of PAP titration is completed, and then at scheduled telephone follow-up calls. After each night of use, the recorded data on usage are transmitted from the participant's home to a central computer using a wireless communication feature in the PAP device. The research team will review the transmitted data and judge its acceptability based on usage for at least 4 hours/night for at least 3 nights during the run-in period. After randomization, PAP data will be visually reviewed to identify the optimal pressure, defined as the pressure that eliminates 90% of airflow limited events.

We recognize that some participants will have less than optimal PAP adherence after enrollment. In participants that use PAP more than 5 h/night during the study, we will provide positive reinforcement regarding their PAP use. In those participants where the use of PAP is poor, we will use Motivational Enhancement Therapy (MET), which is based on the principles of motivational interviewing. Each participant having difficulty with PAP therapy will be asked to provide a subjective assessment of wearing PAP; expected barriers and facilitators of use; and motivation and confidence to use PAP. Issues that are raised will be addressed to improve adherence to PAP.

- 3. Telephone calls:** Participants in both groups will receive a phone call from a research team member twice a month after the first month visit. The goal of these calls is to optimize adherence to the lifestyle intervention and also to PAP therapy. Compliance with diabetic medications will be again emphasized. For those randomized to PAP therapy + HLSE, research staff will identify problems that may impact their use of PAP therapy and then implement solutions (e.g., new mask) that could further improve compliance.

**Study duration and number of study visits required of research participants.**

For the screening portion of the study, each participant will have the following visits: (a) informed consent, (b) PAP run-in phase, and (c) extended-montage sleep study.

After the screening assessments, each participant eligible for randomization will have five visits (randomization, 2 weeks, 1 month, 2 months, and 3 months). To minimize burden, subjects will commence data collection for the CGM and the ambulatory 24 hour blood pressure monitoring at the time of the extended sleep study montage prior to randomization. Finally, because continuous glucose monitoring (CGM) will be conducted for two weeks, participants will exit the study at 3.5 months. During the 2 weeks of CGM, group assignment will remain as at the time of randomization.

## 5. Inclusion/Exclusion Criteria

**Inclusion Criteria:** All participants must be capable of giving informed consent to participate. This study will target type 2 diabetics (age  $\geq 21$  and  $\leq 75$  years) with previously untreated OSA.

**Exclusion Criteria:** As detailed in the Table below, participants will be excluded if they: (1) have any confounding medical condition, (2) are not willing to be randomized, and (3) are unable to provide consent.

### Exclusion Criteria

|   |   |
|---|---|
| Inability to consent or commit to the required visits | Occupation as a commercial driver or operator of heavy machinery                          |
| HbA1c $< 6.5\%$ or $> 10.0\%$                         | Active substance use  |
| Use of insulin or other injections for diabetes       | Untreated thyroid disease   |
| Weight change of 10% in last six months               | Pregnancy   |
| Use of oral steroids in the last six months           | Any history of seizures or other neurologic disease                                       |
| Pulmonary disease (i.e., COPD)                        | Poor sleep hygiene or sleep disorder other than sleep apnea                               |
| Renal or hepatic insufficiency                        | Central sleep apnea   |
| Recent MI or stroke (< 3 months)                      | Variants of obstructive sleep apnea (e.g., REM-related OSA)                               |
| Sleep-related hypoventilation                         | Excessive subjective sleepiness (Epworth score $> 16$ )                                   |
| Obesity-hypoventilation syndrome                      | Participants not suitable for the study based on the clinical judgment                    |
| Morbid Obesity  | Use of any investigational drug within the past 30 days or participating in another study |

## 6. Drugs/ Substances/ Devices

For the current study, PAP therapy device will be used for treatment for OSA. PAP devices are the standard of care for the management of OSA.

## 7. Study Statistics

### a. Primary outcome variable.

- Glycemic Variability (Continuous Glucose Monitoring: CGM)
- HbA1c
- Self-Monitoring of Blood Glucose (SMBG) Profiles

### b. Secondary outcome variables.

- BP, Endothelial Function
  - 24-hr BP profile
  - Endothelial function (Endo-PAT)
- Sleepiness and Quality of Life Assessments
  - Subjective sleepiness (Epworth Sleepiness Scale)
  - Quality of Life (SF-36, SAQLI, FOSQ)

### c. Statistical plan including sample size justification and interim data analysis.

Statistical analyses for the primary evaluation of treatment effects will follow the intention-to-treat paradigm, which means that all randomized patients will be included in the treatment group to which they were assigned. Participants who do not have the requisite data for our primary outcomes will be accounted for and compared by assigned group. Participants not able to be included in the intention-to-treat analyses will be compared to those who are included with respect to demographic and other characteristics. Periodic descriptive summaries of data will be performed to monitor for adverse events and to improve data quality by identifying and investigating outliers in observed measurements.

The primary outcomes for the trial are changes from baseline to 3 months in HbA1c and postprandial hyperglycemia ( $\Delta$ =post-preprandial glucose). Initial analyses will tabulate demographic and baseline characteristics of the participants by randomization group.  $\chi^2$ -tests and one-way ANOVA will be used to compare groups on these characteristics. If differences in some characteristics are observed, even though not statistically significant, these variables will be considered for inclusion in regression models assessing our outcomes. The analytical approach will consist of using mixed model linear regression of the change measure (e.g.,  $\Delta$ HbA1c or improvement in postprandial increment) at 3 months with an indicator variable for the fixed effect for treatment group and baseline value of the measure and adjustment for correlation between baseline and follow-up measures. Additional covariates (e.g., baseline weight and body fat, weight change, sleep duration, activity levels, caloric intake) will be included in the model particularly if the randomization results in serious imbalances in a covariate across treatment groups. More powerful, mixed model repeated measures analyses will also be done using all available longitudinal data on HbA1c and average postprandial-preprandial ( $\Delta$ ) glucose values including rate of change from baseline. The purpose of these analyses is to examine whether the trajectories of our dependent variables vary over time based on the assigned group.

The secondary outcomes include change in: (1) CGM-derived mean glucose values; (2) systolic, diastolic and mean daytime and nighttime BP; (3) heart rate variability derived indices of sympathovagal balance; (4) endothelial function (Endo-PAT derived reactive hyperemia index); (5) markers of oxidative stress (e.g., oxidized LDL); (6) lipid abnormalities (e.g., LDL, HDL, triglycerides); (7) myocardial injury (troponin-I); and (8) renal injury (urinary albumin and creatinine). All analyses for our secondary outcomes will be done under the intention to treat principle. Initial analyses will tabulate baseline characteristics of participants by randomization group. For our continuous outcomes, we will use multivariable regression and mixed model repeated measures analyses as done for the primary outcomes.

Sample Size Determination:

Sample size was calculated based on the magnitude of anticipated improvement in our primary outcome (e.g., standard deviation [SD] of Dexcom CGM glucose values). The primary assumption for determining sample size was an expected mean decrease in SD of CGM glucose values of 3.3 mg/dl (SD: 6.9 mg/dl) with PAP therapy with no expected change in the control group. Assuming a type 1 error and a power of 90%, a sample size of 92 participants would be needed in each arm (total N=184). To account for modest dropout (~10%), the enrollment goal was 102 participants in PAP therapy arm and 102 participants in the control arm. A total sample size of 184 participants would also allow the study to detect a mean HbA1c difference of 0.36% between the two groups. Enrollment began in December 2014 and ended in December 2019 with a final sample size of 186 participants. In response to the COVID19 pandemic, all clinical research activities ended in early March 2020.

d. Early stopping rules.

Not applicable.

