## 1. Abstract

It is estimated that nearly 25.8 million people in the United States have type 2 diabetes mellitus. Research over the last decade has shown that obstructive sleep apnea (OSA) is a common condition in people with diabetes. Data from a number of different studies show that the prevalence of moderate to severe OSA in diabetics is approximately 50%. Observational and experimental evidence also indicates that intermittent hypoxemia and recurrent arousals in OSA may alter glucose metabolism and worsen glycemic control. However, the impact of treating OSA with positive airway pressure (PAP) therapy on glycemic control is not well defined. Adequately powered randomized clinical trials have yet to be performed to demonstrate whether PAP therapy for OSA in diabetics can improve glycemic control, decrease blood pressure, and reverse endothelial dysfunction. The overarching goal of this study is to determine whether PAP therapy for OSA in diabetics with less than optimal glycemic control leads to improvements in (a) glycosylated hemoglobin (HbA1c); (b) glycemic variability as assessed by self-monitoring of blood glucose and continuous monitoring of glucose; (c) blood pressure; and (d) endothelial function. We propose to conduct a randomized control trial in people with diabetes and moderate to severe OSA who will be randomly assigned for 3 months to PAP therapy along with healthy lifestyle and sleep education (PAP-HLSE) or healthy lifestyle and sleep education (HSLE alone).

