## 2. Objectives (include all primary and secondary objectives)

Primary Objectives: To examine whether treatment of OSA with PAP in diabetics has favorable effects on glycemic control, postprandial hyperglycemia, and glycemic variability.

Secondary Objectives: To assess whether treatment of OSA with PAP in diabetics improves 24-hr blood pressure and endothelial function.

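### Section 7c names HbA1c and postprandial increment as the primary outcomes but sizes the trial on the SD of CGM glucose, and nothing says which result decides the trial

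*Combined protocol and SAP*

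**What the plan says.** Five places in the combined protocol and SAP bear on what is primary.

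- **Section 7c, analysis text:** "The primary outcomes for the trial are changes from baseline to 3 months in HbA1c and postprandial hyperglycemia". The second is defined as postprandial minus preprandial glucose. CGM variability is not named.
- **Section 7c, sample size:** "Sample size was calculated based on the magnitude of anticipated improvement in our primary outcome (e.g., standard deviation [SD] of Dexcom CGM glucose values". The effect is a 3.3 mg/dl decrease with SD 6.9 mg/dl and no change in controls, giving 92 per arm at 90% power. It adds: "A total sample size of 184 participants would also allow the study to detect a mean HbA1c difference of 0.36% between the two groups". No HbA1c SD is given, and postprandial increment is not mentioned.
- **Section 7a:** three unranked variables: "Glycemic Variability (Continuous Glucose Monitoring: CGM" (no metric given there), HbA1c, and "Self-Monitoring of Blood Glucose (SMBG) Profiles".
- **Section 2:** the primary objectives concern "favorable effects on glycemic control, postprandial hyperglycemia, and glycemic variability", also unranked.
- **Section 1:** the abstract refers to "glycemic variability as assessed by self-monitoring of blood glucose and continuous monitoring of glucose", which makes SMBG a measure of variability, whereas the analysis text is concerned with postprandial increment.

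The only CGM measure in section 7c's list of secondary outcomes is mean glucose, which is not the SD.

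**The concern.** A reader cannot tell which comparison the trial stands or falls on.

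- If the analysis text governs, the outcome for which 90% power is demonstrated is not a deciding outcome.
- If the sample-size text governs, the analysis text omits the deciding outcome.
- If several primaries are intended, neither the overall false-positive chance nor the overall power can be stated without a decision rule.

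A mixed result, such as an improved CGM SD with unchanged HbA1c, could be called a success under one paragraph and a failure under another.

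Timing adds weight. The sample-size text reports "Enrollment began in December 2014 and ended in December 2019 with a final sample size of 186 participants", so it was written or edited after enrollment closed. The documents do not show when any primary outcome was fixed.

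**Working it through.** **1. The sections side by side**

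| Place | HbA1c | Postprandial increment | CGM variability |
|---|---|---|---|
| Section 2 | as glycemic control | yes | as glycemic variability |
| Section 7a | yes | only if SMBG profiles mean this | yes, no metric |
| Section 7c, analysis text | yes | yes | no |
| Section 7c, sample size | detectable difference, no SD | no | SD of Dexcom glucose, 90% power |

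**2. Reproducing 92 per arm.** Inputs from section 7c: difference 3.3, SD 6.9, power 90%. No alpha value is printed; two-sided 0.05 is assumed. Normal approximation:

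n = 2 × (1.960 + 1.282)² × (6.9/3.3)² = 91.9, so 92 per arm.

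The figure reproduces. The same formula needs 109 per arm at two-sided 0.025 and 119 at 0.0167. The stated size therefore spends the whole 0.05 on CGM SD and leaves no allowance for further primaries.

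**3. Two possible decision rules.** The documents give no correlation between outcomes, so a range is shown, using equicorrelated normal test statistics. With k outcomes at correlation 0, the any-one-counts error is 1 − 0.95^k and the all-must-succeed power is 0.90^k. For other correlations, the same probabilities come from the multivariate normal. The power rows suppose that every effect is real with 90% power, which the plan shows only for CGM SD.

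| | correlation 0 | 0.5 | 0.9 |
|---|---|---|---|
| Any one counts, false-positive chance, 2 outcomes | 9.75% | 9.07% | 7.04% |
| Any one counts, false-positive chance, 3 outcomes | 14.26% | 12.54% | 8.36% |
| All must succeed, joint power, 2 outcomes | 81.0% | 83.2% | 86.9% |
| All must succeed, joint power, 3 outcomes | 72.9% | 78.2% | 85.0% |

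The all-must-succeed rule does not inflate the error rate.

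**4. What the HbA1c statement implies.** Solving for the SD at 92 per arm:

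SD = 0.36 / [(1.960 + z) × √(2/92)], which is 0.75% at 90% power (z = 1.282) and 0.87% at 80% (z = 0.842).

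The ordinary reading is that the same 90% applies. No HbA1c SD is printed against which to check either value.

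**5. Cost to CGM SD of a Bonferroni split at 92 per arm.** Unadjusted, the standardized effect is 3.3 / (6.9 × √(2/92)) = 3.24. Power is Φ(3.24 − 2.241) = 84.2% for two outcomes and Φ(3.24 − 2.394) = 80.2% for three.

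The plan also adjusts for baseline. If 6.9 is the SD of change, and variances at baseline and follow-up are equal, the residual SD is 6.9 × √((1 + r)/2), where r is the baseline–follow-up correlation (not given):

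| r | 0.3 | 0.5 | 0.7 | 0.9 |
|---|---|---|---|---|
| Two outcomes | 96.3% | 93.4% | 89.9% | 86.1% |
| Three outcomes | 94.8% | 91.2% | 87.0% | 82.5% |

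**The case against.** The best defence is that the trial has three primaries, as sections 2 and 7a say, and that the analysis text merely leaves one out. CGM variability is indeed primary in those sections, so the conflict is between the analysis text and the rest of the document. This reading still supplies no decision rule, and it means that the paragraph defining the analysis omits the outcome on which the trial was sized.

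Second, HbA1c does have a detectable difference, ordinarily read as at 90% power. That stands as far as it goes: the HbA1c claim is stated but cannot be checked without an SD. For postprandial increment, a power statement is absent altogether.

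Third, the SMBG ambiguity is small. Section 4 describes a profile with preprandial and 2-hour postprandial readings at each meal, which points to SMBG as the source of the increment. The abstract points the other way, so one clarifying line is enough.

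Fourth, the error rates and joint powers are conditional on rules the plan never states, and with baseline adjustment a Bonferroni split need not bring power below 90%. This is correct. The harm established is ambiguity about the deciding result, not a demonstrated error rate or loss of power.

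**Conclusion.** The concern holds and must be fixed. Section 7c contradicts itself on the primary outcome, and no other section resolves it. The arithmetic behind 92 per arm is sound for CGM SD under two-sided 0.05; the defect is that the analysis text does not count that outcome as primary.

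The consequence depends on the rule eventually adopted: a false-positive chance of up to 14.3% if any of three outcomes could be claimed at 0.05 each, or joint power as low as 72.9% if all three were required at 90% each. Both extremes assume independent outcomes, and both shrink as correlation rises. Confidence in the contradiction itself is high, because it rests on the text alone. There is no finding that the primary outcome was switched; the documents do not bear on that.

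**What to change.** First establish, from a dated record made before any treatment comparison, which outcome was primary. Keep that one and bring sections 2, 7a and 7c, including the sample-size text, into line with it.

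- **If it was CGM SD:** name it in the analysis text without the *e.g.*, and carry the metric into section 7a. State the sensor (section 4 has participants wear both Dexcom and Abbott), whether the SD is total or within-day, and the recording window (month 3 to 3.5, since section 4 has participants exit after two weeks of CGM). Make HbA1c and postprandial increment key secondary outcomes.
- **If it was HbA1c, postprandial increment or both:** restate the power for each with its SD, and describe the CGM SD calculation as supporting.
- **If several primaries are kept:** state the rule. For any-one-counts, add a multiplicity adjustment and restate the power. For all-must-succeed, restate the joint power.
- **In every case:** say whether the SMBG profiles in section 7a mean postprandial increment.
- **If no such record exists:** state when the primary was fixed and whether treatment comparisons had been seen by then; if they had, report it as post hoc.

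The cost is protocol and SAP wording plus retrieval of a record, with no new data. The downside is that an outcome may lose its primary label or the stated power may fall; enrollment has ended, so the sample size cannot be raised to compensate.

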#### **Procedures to be conducted as part of the clinical trial:**

1. **Questionnaires:** Basic demographic factors (race, marital status, education, work status, smoking history, alcohol history, and caffeine consumption), sleep-related symptoms, and prevalent medical conditions will be assessed with the Medical History and Sleep Survey. Quality of life will be ascertained using the Medical Outcomes Short-Form 36 (SF-36), Functional Outcomes of Sleep Questionnaire (FOSQ), and the Sleep Apnea Quality of Life Index (SAQLI). To determine a participant's habitual activity level, the Minnesota Leisure Time Physical Activity Questionnaire (PAQ) will be used. Time points for data collection: Before randomization and 3 months.
2. **Anthropometry:** Standard methods will be employed for measurements of weight, height and for neck, waist, and hip circumferences. For example, measurement of neck circumference will be performed by using an inelastic tape that is applied around the neck just below the laryngeal prominence. Waist circumference will be measured at the narrowest part of the torso, at the end of normal expiration. For

obese participants, the smallest horizontal circumference between the ribs and the iliac crest will be measured. Hip circumference will be measured around the buttocks in a horizontal plane at the level of the maximal extension of the buttocks. Time points for data collection: Before randomization and 3 months

3. **Clinic Blood Pressure:** Resting arm blood pressure will be obtained in triplicate using a conventional mercury sphygmomanometer. Cuff size will be determined by measuring the circumference of the upper arm, measured at the midpoint, and identifying the appropriate bladder size from a standard chart. Measurements will be repeated three times and recorded. Time points for data collection: Time points for data collection: Before randomization, 2 weeks, 1 month, 2 months, and 3 months.
4. **24 Hour Blood Pressure:** Participants will be instructed in the use of a 24 hour ambulatory blood pressure monitor. The device consists of a blood pressure cuff that is connected by rubber tubing to a small pressure monitoring device that weighs only 9 oz and fits easily in a shirt pocket. The device will be programmed to measure blood pressure at hourly intervals for the subsequent 24 hours. Time points for data collection: Before randomization and 3 months

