8. **Endothelial Function Using Peripheral Arterial Tonometry (PAT):** PAT will be measured using the Endo-PAT device (Itamar Medical). This test requires approximately 20 minutes and is performed with participants positioned supine in a quiet environment with dimmed lighting. The participant is asked to remove rings and whether they have allergies to latex. Fingernails are trimmed if overly long. Probes (one-time use only) are then placed on the index finger of each hand. A blood pressure cuff is placed on the non-dominant arm. Following a brief period (5 minutes) of baseline recordings, the cuff is inflated to 60 mmHg above their systolic blood pressure determined earlier (to at least 200 mmHg but not more than 300 mmHg) to occlude blood flow in the arm. The period of occlusion is timed with a stop watch for 5 minutes. At exactly 5 minutes, the pressure is rapidly released and readings taken for a minimum of 5 minutes. Once recording is complete, the probes are removed and discarded. Time points for data collection: Before randomization and 3 months.
9. **Assessment of Body Fat:** Total body fat, a major confounder in the relationship between sleep disturbance and glycemic control, will be obtained using Dual-Energy X-Ray Absorptiometry (DEXA) scan. The

DEXA scan is used to measure body composition in terms of fat and fat-free mass. DEXA systems are used to perform whole-body scans in order to determine the bone and soft tissue composition of the whole body and subregions such as arms, legs, and trunk. The body is partitioned into three segments: bone, fat, and fat-free mass. A total body scan takes 6 minutes and the radiation dose incurred during DEXA scanning is approximately 0.5 millirem, which is a very small dose. DEXA is a simple and safe technique that is routinely performed in clinical care and imposes minimal participant burden. Time points for data collection: Before randomization and 3 months.

**10. Food Diary:** All participants will be required to document their dietary intake for 3 days during the acquisition of the 7-point SMBG and CGM data. Time points for data collection: Before randomization and 3 months.

**11. Home sleep monitoring:** At the 3 month visit, home sleep testing will be repeated (ApneaLink®) and also the actigraph as done during the screening phase.

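### Weight change, most naturally read as an on-study variable that PAP may affect, is listed as a covariate for the primary-outcome model, and no model is named as primary

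*Combined protocol and SAP*

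**What the plan says.** Section 7c describes a mixed linear model for the change at 3 months, "with an indicator variable for the fixed effect for treatment group and baseline value of the measure". The next sentence widens it: "Additional covariates (e.g., baseline weight and body fat, weight change, sleep duration, activity levels, caloric intake) will be included in the model", and continues "particularly if the randomization results in serious imbalances in a covariate across treatment groups". The covariate list is illustrative, and the stress on imbalance does not restrict inclusion to that case.

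Intention-to-treat is defined in the same section as a rule about grouping, "which means that all randomized patients will be included in the treatment group to which they were assigned". It does not fix the covariate set. Section 7c does not say which covariate set is primary, and it does not call any adjusted model sensitivity, exploratory or mediation.

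On timing, section 4 (Anthropometry) says "Standard methods will be employed for measurements of weight, height and for neck, waist, and hip circumferences", with collection before randomization and at 3 months. The only other mention of weight change as a variable is an exclusion criterion in section 5: "Weight change of 10% in last six months".

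**The concern.** A covariate measured after randomization can be affected by treatment. Conditioning on it changes the question from the total effect of assignment to PAP to the effect at equal weight change. If weight change and HbA1c change also share unmeasured causes, the coefficient need not match even the direct effect.

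The plan's main reason for adding covariates does not fit this one. Randomization can leave a chance imbalance in baseline weight. It cannot do so in a change that has not yet happened. A difference between arms in on-study weight change arises later, by chance or through treatment.

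The documents do not say that PAP changes weight. They do make a link between weight and glucose plausible. Section 4 calls body fat "Total body fat, a major confounder in the relationship between sleep disturbance and glycemic control", and both arms receive lifestyle guidelines for "disease prevention and weight loss will be provided to all subjects". With a positive weight–HbA1c slope, adjustment overstates the benefit if PAP raises weight and understates it if PAP lowers weight. A negative slope reverses this.

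Because no covariate set is ranked first, the choice between adjusted and unadjusted estimates could also be made after the results are seen.

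**Working it through.** **The plan's own figure.** Section 7c gives a 3.3 mg/dl difference, SD 6.9 mg/dl, 90% power and 92 per arm. The alpha value is not stated; two-sided 5% is assumed. n = 2 × (1.960 + 1.2816)² × (6.9/3.3)² = 91.9, so 92 per arm. This reproduces the stated figure.

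**Implied SD of HbA1c change.** Section 7c says the same sample detects 0.36% but attaches no power to that figure. Assuming 90%, SD = 0.36 / (3.2415 × √(2/92)) = 0.753. Assuming 80%, it is 0.871.

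**Shift from adjusting.** Adjusted estimate = total effect − (arm difference in weight change, PAP minus control) × (within-arm slope of HbA1c change on weight change). The differences and slopes below are assumptions; the documents give neither.

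- 0 kg, any slope: no shift
- 0.5 kg × 0.05% per kg = 0.025 points; 0.025/0.36 = 7%
- 1 kg × 0.075% per kg = 0.075 points; 21%
- 1.5 kg × 0.10% per kg = 0.15 points; 42%

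**Effect on the test.** Simulation with 92 per arm, 6,000 replicates, true total effect −0.36 and SD 0.753. The SD of weight change is also assumed (2.5, 3.5 or 4.5 kg). Power without weight change in the model is 90%.

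| Arm difference (kg) | Slope (% per kg) | Adjusted estimate | Power at SD 2.5 / 3.5 / 4.5 kg |
|---|---|---|---|
| 0 | 0.05 | −0.36 | 91 / 91 / 92% |
| 0 | 0.10 | −0.36 | 93 / 96 / 98% |
| −0.5 | 0.05 | −0.335 | 86 / 87 / 88% |
| −1 | 0.075 | −0.285 | 73 / 77 / 81% |
| −1.5 | 0.10 | −0.21 | 48 / 55 / 64% |
| +1 | 0.075 | −0.435 | 98 to 99% |

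Monte Carlo error is at most 0.7 percentage points for power.

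**Closed-form check of the −1 kg row at SD 3.5 kg.** Residual SD = √(0.753² − (0.075 × 3.5)²) = 0.706. SE = 0.706 × √(2/92) × √(1 + (1/3.5)²/4) = 0.105. Then 0.285/0.105 = 2.71, which gives power of about 77%.

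**Type I error.** If the total effect is zero, the arms differ by 1 kg in either direction and the slope is 0.075 (SD 3.5 kg), the adjusted test rejects about 11% of the time. With no arm difference it rejects 5%.

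**Other SD.** With SD 0.871 the shifts in points are the same. Power in the −1 kg row is 61 / 63 / 66%, against 80% without weight change in the model.

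**Shared causes.** The bias does not need weight to cause HbA1c change. With no causal effect of weight and a correlation of 0.35 from a common cause (SD 3.5 kg), a 1 kg difference gives −0.436 (PAP raises weight) or −0.285 (PAP lowers it). With no arm difference there is no bias.

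In a second example weight has a causal slope of 0.10 and the arm difference is +0.5 kg. A common cause adds 1.5 kg and 0.3 points per SD, and the other variation in weight has SD 2 kg. The total effect is −0.36 + 0.05 = −0.31. The within-arm slope is 0.10 + 0.45/6.25 = 0.172. The adjusted estimate is −0.31 − 0.5 × 0.172 = −0.40, which is neither the total effect (−0.31) nor the direct effect (−0.36).

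**The case against.** The strongest reply is that the plan already has a default model. Treatment arm and baseline value come first, and weight change appears only afterwards, as one example, mainly for cases of imbalance. A fair reader could take the first model as primary. But the plan does not say so, and the covariates go into that same model, not a supplementary one.

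The term may also mean change before enrollment, which section 5 uses as an exclusion. That reading would explain why imbalance is the trigger. It is the weaker reading, because section 5 does not describe that change as a recorded covariate, while weight is measured at both ends of the trial. It cannot be ruled out, so the plan should say which is meant.

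The size does rest wholly on assumed inputs. With no PAP effect on weight, adjustment is harmless and slightly helpful. The 42% shift and the 48% to 64% power need both extremes together. The power loss belongs to the adjusted coefficient; the arm-plus-baseline model keeps about 90% throughout. The benchmark of 0.36% is also not the figure that set the sample size, and nothing is quantified for postprandial glucose or CGM variability. These points limit what can be said about size. They do not give a reason to leave the covariate in an unranked model.

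It is also fair that naming one covariate set does not settle everything. Section 7c has a looser rule that makes any observed baseline difference, significant or not, a reason to consider a covariate. Its repeated-measures analyses have no rank either.

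**Conclusion.** The concern holds and should be fixed. On its natural reading, the plan allows a post-randomization variable into the model for its primary outcomes, on a rationale that cannot apply to that variable, and does not say which model is primary. The intention-to-treat rule as written is not broken, and the arm-plus-baseline estimate is unaffected.

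The size ranges from zero, if PAP does not change weight, to an amount the documents cannot supply. At the midpoint of the assumed range (1 kg, 0.075% per kg) the shift is 0.075 points, 21% of 0.36%, in either direction. This rests on the assumed weight difference and slope. The power figures rest further on two-sided 5% alpha, 90% power for the 0.36% figure and the assumed spread of weight change.

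For sleep duration, activity levels and caloric intake the problem is ambiguity only. Section 4 has them collected both before randomization and at 3 months, and section 7c does not say which values enter the model. Section 7c analyses the secondary outcomes by the same methods, so the covariate list probably carries over, though that is an inference.

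**What to change.** - Delete weight change from the covariates of the primary model, or report it only in a separate analysis labelled exploratory (mediation). If change before enrollment was meant, say so.
- Name as primary the model with treatment arm and baseline value of the outcome, plus pre-randomization covariates only. Listing those covariates in advance, instead of choosing them on observed imbalance, and stating the rank of the repeated-measures analyses would close the remaining gaps.
- State that sleep duration, activity levels and caloric intake enter as pre-randomization values.
- Apply the same rule to the secondary outcomes.

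Section 7c reports that enrollment ended in December 2019, so the change should precede any unblinded analysis. If that analysis is already done, report the named model as primary and say that the choice was made afterwards. The change then improves the reporting but cannot restore pre-specification.

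The cost is a few sentences. The baseline values are already collected, and the sample size does not change. If PAP does not affect weight, some precision is given up: about 1 to 2 points of power at 0.05% per kg, and 3 to 8 points at 0.10% per kg, under the assumptions above.
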